- c. *Recruitment methods to be applied specifically to students and/or employees. If the same recruitment methods previously described in the protocol will be used, then state that:* Any student or employee interested in participating should email [name] regarding their interest. The PI will not directly solicit any employee to participate.
- d. *Additional safeguards included to protect the rights and welfare of students and employees:* The CVC research manager will verify with interested employees that they understand participation in the study is voluntary and that actions made towards participating were voluntary.
- e. *Protections to ensure that a subject's decision about participation and/or early withdrawal from the study will not affect his/her status as a student or employee:* The informed consent form states that participation and/or early withdrawal from the study will not affect a subject's status as a student or employee.
- f. *Check to confirm that you have submitted a letter from the appropriate institutional official (e.g., Department Chair, Dean, Vice-President) who oversees the students and/or employees attesting to the fact that the employee's or student's participation in the research is acceptable and that coercion has been minimized.*

H. Adverse Event Monitoring

H.1 Definitions

Define adverse events (AEs), serious adverse events (SAEs), and unanticipated problems for your study:

Adverse event (AE):

- 1) A new event which was not pre-existing at initial study drug administration.
- 2) A pre-existing event which recurs with increased intensity or increased frequency subsequent to study drug administration.
- 3) An event which is present at the time of study drug administration which is exacerbated following initial study drug administration.

Serious Adverse Event (SAE):

- 1) Death
- 2) Life-threatening adverse drug experience
- 3) Inpatient hospitalization or prolongation of existing hospitalization (for > 24 hours)
- 4) Persistent or significant incapacity or substantial disruption of the ability to conduct normal life functions
- 6) Important Medical Event (IME) that may not result in death, be life threatening, or require hospitalization may be considered a serious adverse drug experience when, based upon medical judgment, it may jeopardize the patient or subject and may require medical or surgical intervention to prevent one of the outcomes listed in this definition

Unanticipated problems

- 1) Any experience when, based upon medical judgment, it may jeopardize the patient or subject and may require medical or surgical intervention to prevent one of the outcomes listed in this definition

H.2 Reporting Procedures

1. Describe the protocol-specific reporting procedures, including who will be responsible for each step (e.g., PI, Data Coordinating Center, Medical Monitor), which forms should be completed, timeframes for reporting, how reports will be distributed, and what follow-up is required: Any events, although not anticipated, will be reported to the IRB.
2. Include specific details of reporting procedures for:
 - a. Deaths, life-threatening events, pregnancies: Any events, although not anticipated, will be reported to the IRB.
 - b. Other SAEs: Any events, although not anticipated, will be reported to the IRB.
 - c. Other AEs: Any events, although not anticipated, will be reported to the IRB.
 - d. Other UPs: Any events, although not anticipated, will be reported to the IRB.

Ensure that the reporting procedures meet the reporting requirements of the FDA, NIH, OHRP, sponsor, study leadership and any other regulatory body that applies to the study, as applicable.

H.3 Reportable New Information

Check to confirm that reportable new information will be reported to the IRB per the Tufts Health Sciences IRB's [Reportable New Information policy](#). If your reporting plan to the IRB differs from the IRB's policies, please describe it in detail or specify where this information is in the protocol:

I. Statistical Considerations

I.1 Study Endpoints

1. Describe the primary and secondary study endpoints:

Primary DXA endpoint: fat free mass (FFM) measured by DXA

Primary ultrasound endpoint: FFM measured by BodyMetrix ultrasound

2. Describe any primary or secondary safety endpoints: N/A

I.2 Statistical Analysis

1. Describe the statistical analyses that will be performed for this study: Bland-Altman plot with bias and precision statistics to define the limits of agreement for FFM measured by DXA and ultrasound techniques.
2. Provide a power analysis: We previously showed good correlation between DXA and deuterium methods of FFM measurement in 8 patients with HF. Therefore we are aiming for a minimum enrollment of 60 subjects (10 per cohorts A-C, 30 per cohort D) and a maximum of 90 subjects total.

I.3 Number of Subjects

1. Specify the number of subjects to be enrolled in total across all sites: 90 or N/A this is not a multicenter study.
2. Specify the number of subjects to be enrolled at the Tufts site. Subjects who sign an ICF are considered "enrolled". For studies that have a separate screening ICF, this number is the number of subjects who sign a screening ICF: 90
 - a. Provide the rationale for enrolling this number of subjects at the Tufts site: We plan to recruit a minimum of 60 subjects (10 per subgroups A-C, 30 per subgroup D) and a maximum of 90 subjects total.
 - b. Estimate the number of subjects expected to be enrolled at the Tufts site (i.e. sign the screening or study ICF) as well as the number needed to complete the study at the Tufts site: 90
 - c. If a large number of withdrawals and/or dropouts is expected, explain why: N/A

I.4 Data Management

1. Describe the data analysis plan, including descriptions of the data: Bland-Altman plot with bias and precision statistics to define the limits of agreement for FFM measured by DXA and ultrasound techniques. For skeletal muscle ultrasound to be considered a valuable technique for assessment of cachexia/sarcopenia, we would require the mean differences between the US and DXA measurement methods to be less than +/- 3, which is in line with our validation of DXA measurement of fat-free mass using the deuterium reference technique.
2. Provide a power analysis: See above
3. Describe the steps that will be taken to secure the data (e.g., training, authorization of access, password protection, encryption, physical controls, certificates of confidentiality, and separation of identifiers and data) during storage, use, and transmission: The data will be stored only on Tufts MC networked folders with password protection and accessed within accessed-controlled academic hospital areas.
4. Describe any procedures that will be used for quality control of collected data: Review of data by PI
5. Describe how data and specimens will be handled study-wide as follows:
 - a. What information will be included in that data or associated with the specimens: Subject number, sex, age, weight, body mass index, heart failure status.
 - b. Where and how data or specimens will be stored: N/A
 - c. How long the data or specimens will be stored: N/A
 - d. Specify who will have access to the data or specimens: Research team members only
 - e. Specify who is responsible for receipt or transmission of the data or specimens: N/A
 - f. Specify how data and specimens will be transported: N/A
 - g. Specify the plan for study data retention and storage (accounting for research team turnover): The data will be stored for at least 7 years after completion of the study.

I.5 Randomization

Will subjects be randomized?

Yes No Yes No

J. Drugs or Devices

1. Will the research involve drugs?

Yes No

Yes No

2. Will the research involve devices?

BodyMetrix Pro body composition ultrasound device

Yes No

If Yes to either, respond to all of the following:

1. Who on the research team, in addition to the Principal Investigator, will be accountable for drug(s)/device(s): [name], [name], [name] (all team members) are all trained on the BodyMetrix Ultrasound device and accountable for secure storage
2. Who will interface with the pharmacy (drugs) or sponsor (devices): [name] interfaces with device vender (Intelametrix, Brentwood, CA) for any ultrasound device questions. There is no device sponsor or drug.
3. If pre-printed orders will be created to obtain study drug(s) from the pharmacy, describe the procedures for reviewing and verifying the accuracy of the pre-printed orders prior to their being implemented: or N/A, there are no pre-printed orders

4. *If computerized order sets are created and/or infusion devices need to be programmed to administer an investigational drug, indicate the mechanism to pre-review and verify their accuracy, including who will be involved in this process from the research team, pharmacy, and nursing:* _____ or N/A, there are no computerized orders sets and/or infusion devices.
5. *The study drug, device, or procedure (including beneficial health care procedures) will be available to subjects after participation in the study:* Yes N/A
6. *There are medications or other substances that should not be taken while participating in the study. A list of these are incorporated into the ICF a subject handout:* Yes N/A
7. *Handouts or instructions sheets that will be given to subjects on how to administer study drug(s) or use study device(s) have been submitted to the IRB:* Yes N/A

K. Study Administration

K.1 Setting

1. *Describe the sites / locations where your research team will conduct the research:* South 6 cardiology clinic, CTRC, cardiology inpatient areas e.g. CCU, Pratt 8, North 6.
2. *The research will take place at an international site, and the [International Guidance](#) and [International Checklist](#) were utilized:* Yes N/A

K.2 Registration

1. *Describe the steps the research team will take to ensure that a subject is appropriately enrolled or registered in the study prior to receiving any study intervention (e.g. describe and submit any protocol eligibility checklist that will be used, specify who on the research team will confirm eligibility and that consent was documented, etc.):* N/A

K.3 Resources Available

1. *Describe the roles/tasks of each research team member here (or alternatively, you may submit any current Delegation of Authority Log you may have which already has this information completed):* [name]: Research Coordinator - arranges study visits, accompanies subjects to DXA, performs ultrasound
[name]: Research Coordinator - arranges study visits, accompanies subjects to DXA, performs ultrasound
[name]: PI – performs consent, oversees research activities, performs ultrasound, performs analyses
[name]: Co-I – arranges study visits, performs ultrasound, performs analyses
2. *Describe the qualifications (e.g., training, experience) of the PI and research team to perform their roles. Provide enough information for the IRB to determine the PI and research team are qualified to conduct the proposed research. Alternatively, you can submit the current CVs for the research team instead:* CVs submitted
3. *Describe the coverage plan to address any issues (including subject safety issues) that occur while the PI is away and/or unavailable. The research team member designated to serve as the acting PI in the PI's absence should have similar training and expertise as the PI:* No study visits will be performed when the PI is unavailable.
4. *Describe the process to ensure the research team members have adequate oversight and are adequately trained regarding the protocol, study procedures, and their roles and responsibilities:* PI meets with the study team weekly to review enrollment, visits, data and subject safety.
5. *Medical or psychological resources that subjects might need, such as for emergencies or medical issues, are available for the study:* Yes N/A

K.4 IRB Review

1. Check to confirm that an appropriate IRB registered with the OHRP, will review and approve this study.
2. Check to confirm that any amendments to the protocol or informed consent documents will be reviewed and approved by the IRB prior to use, unless required to eliminate an apparent immediate hazard to subjects.

K.5 Multi-Site Research

Is this a multi-site study where Tufts is the sponsor, primary grant recipient, or coordinating site?:

Yes No Yes No

K.6 Community-Based Participatory Research

Note: “Community-based Participatory Research” is a collaborative approach to research that equitably involves all partners in the research process and recognizes the unique strengths that each brings. Community-based Participatory Research begins with a research topic of importance to the community, has the aim of combining knowledge with action and achieving social change to improve health outcomes and eliminate health disparities.

Can or will this study involve community-based participatory research?

Yes No Yes No

K.7 Sharing Results with Subjects

Will results (overall study results or individual subject results, such as results of investigational diagnostic tests, genetic tests, or incidental findings) be shared with subjects or others (e.g., the subject’s primary care physician or the subject’s treating physician)?

Yes No Yes No

If Yes, respond to all of the following:

1. *Rationale for sharing these results:* To inform subjects of their current body composition and engage their interest in participation.
2. *How results will be shared:* A paper sheet (template provided) reporting body composition testing by the two methods.
3. *For individual subject results, specify if subjects have the option to opt-in or opt-out of receiving these results or allowing these results to be shared with others:* Subjects can opt out of receiving their body composition results by verbal request.
4. *Any referral policies (i.e. for confirmation of any individual subject results):* The PI will review any very abnormal body composition results with the Registered Dietician on the heart transplant team who oversees each subject’s nutritional consultation during standard of care and can advise on nutritional approaches towards weight gain or loss.
5. Check to confirm that testing of research specimens is being conducted in a laboratory certified (CLIA-approved) to conduct diagnostic testing. If patient-specific research results are reported from the laboratory and those results will or could be used for the diagnosis, prevention, or treatment of any disease or impairment, or the assessment of the health of human beings, the laboratory must be [CLIA certified](#).

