Having demonstrated that sarcopenia can be reversed with LVAD implantation for patients with end-stage HF, the next step is to determine how early sarcopenia onset occurs within the natural history of systolic HF and develop an effective intervention for patients with less advanced HF. It is likely that an optimal intervention to reverse skeletal muscle mass in patients with HF will require elements of muscle substrate provision, anti-inflammatory activity and a pro-anabolic stimulus, and will probably be implemented early in the muscle loss trajectory. DXA is not an ideal technique for measuring changes in skeletal muscle mass during a sarcopenia reversal clinical trial because it is not widely available across medical centers. We also recognize that to bring sarcopenia diagnosis and treatment to the wider population of patients with systolic HF we must develop a method for inexpensive, bedside quantification of skeletal muscle mass to replace the current use of dual-energy X-ray absorptiometry (DXA). Therefore we seek to determine the utility of skeletal muscle ultrasound (US) as a novel method for sarcopenia diagnosis in patients with heart failure, given its

promising data in elderly patients with sarcopenia. Takai et al. (2014) compared skeletal muscle mass measurements by ultrasound to those acquired by DXA scan in 77 elderly subjects. They generated a regression equation using several anatomical ultrasound muscle thickness measurements to predict muscle mass measured by DXA. Ultrasound measurements of skeletal muscle have been evaluated in 2 systematic reviews (Nijholt 2017, English 2012) and have shown good performance for the prediction of lean mass. We hypothesize that DXA measurements of appendicular lean mass (ALM) will show adequate agreement with skeletal muscle US in systolic HF patients for deployment in our future HF body composition studies.

4. *Describe the relevance and usefulness of the objectives:* Measuring muscle mass will allow us to identify patients with HF who are experiencing muscle wasting. Comparing DXA scan and ultrasound measurements will demonstrate the validity of ultrasound method as a primary method for measuring muscle mass. The use of muscle ultrasound as a portable and non-ionizing screening method furthers our efforts to pursue effective therapies for cardiac cachexia.

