 5. Are there any risks to study investigators or staff performing the study procedures due to research with high risk populations (e.g. prisoners, intravenous drug users, patients with major psychiatric issues, etc.):?

Yes No Yes No

B.3 Potential Benefits to Subjects

1. Describe the potential benefits that individual subjects may experience from taking part in the research. Include the probability, magnitude, and duration of the potential benefits: There are no direct benefits to individual subjects; however, subjects will obtain information regarding their body composition, which they may find interesting.

Note: Payments and incentives are not considered benefits in the IRB's risk-benefit assessment; payment and incentives should be addressed in the payment section.

2. Check if there is no direct benefit.
3. Describe any benefit to the population from which the subject is drawn: This study will determine if the use of the hand-held ultrasound is comparable to that of the DXA scan. Current AHA LVAD Body Composition subjects must walk or be wheel-chaired to the HNRCA at [name] to undergo the DXA scan. If this study proves the ultrasound applicable for muscle mass measurements, it will provide a less strenuous method of measuring muscle mass for the Body Composition Study. or N/A
4. Describe any benefit to science, society, and humanity in general: This study will validate the applicability of ultrasound muscle thickness measurements as a method to evaluate muscle mass. This will provide the cardiology community with a quicker, non-intrusive, patient-friendly method of measuring muscle mass in this patient population. or N/A

B.4 Alternatives

1. Describe alternatives to participating in this research study (e.g. to decide not participate in the study, alternative treatments, no treatment (palliative care), etc.): Subjects can decide not to participate in the study.
2. Describe the standard clinical care that may be an alternative: or N/A
3. Describe how the subject can receive the research procedures/drug/device used in this study in a non-research setting: or N/A

C. Objectives

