1. Describe the purpose, specific aims, or objectives of the study (i.e. the reason for performing the study in terms of the scientific question to be answered): The primary objective of this study is to validate the use of ultrasound muscle thickness measurements to determine muscle mass. The secondary aim of this study is to use accurate muscle mass measurements to categorize patients as cachectic or sarcopenic.

Note: Specify which are the primary or secondary aims or objectives of this study as applicable. The primary objective is the main question. Secondary objectives are goals that will provide further information for the study.

D. Enrollment and Withdrawal

D.1 Inclusion Criteria

1. Describe the criteria that define who will be **included** in the study as a numbered list:
2. Inclusion criteria:
 1. Cohort A: Healthy volunteers (who may be employees)
 - 18+ years
 - No history of heart failure
 - Not pregnant
 - Willing to take a urinary pregnancy test if there is a possibility of pregnancy
 - Able to freely provide informed consent

2. Cohort B: Participants in the LVAD (left ventricular assist device) body composition study (#12026) who consent to undergo skeletal muscle ultrasound the same day as an LVAD body composition study visit that already includes the DXA and handgrip strength procedures
 - Meet the eligibility criteria outlined in study #12026
3. Cohort C: Outpatients with heart failure, an LVAD or heart transplantation
 - 18+ years
 - Not pregnant
 - Willing to take a urinary pregnancy test if there is a possibility of pregnancy
4. Cohort D: Inpatients with heart failure, an LVAD or heart transplantation
 - 18+ years

Not pregnant

D.2 Exclusion Criteria

1. Describe the criteria that define who will be **excluded** in the study as a numbered list:
2. Exclusion criteria:
 1. Patients requiring temporary mechanical circulatory support
 2. Pregnant women, or women who report there is a possibility they could be pregnant and decline to complete a pregnancy test
3. Describe in detail how the eligibility criteria will be assessed and satisfied (e.g., medical record review, physical examination): **The eligibility criteria will be assessed by medical record review.**
4. State who will determine eligibility. Note that those who are designated to determine eligibility must have appropriate training, expertise, and oversight, for example a physician PI or Co-I on a biomedical study: **[name] will determine eligibility.**

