¹ **Undue influence**, often occurs through an offer of an excessive or inappropriate reward or other overture in order to obtain compliance. For example, an investigator might promise psychology students extra credit if they participate in the research. If that is the only way a student can earn extra credit, then the investigator is unduly influencing potential subjects. If, however, she offers comparable non-research alternatives for earning extra credit, the possibility of undue influence is minimized.

4. *To whom payment will be made (subject, parent [which one], legally authorized representative):*
5. *Payment schedule:*
 - a. *When payment will occur:*
 - b. *The payment schedule (amount at each time point), including details about the payment schedule and amount for subjects who withdraw or are withdrawn from the study:*

D.4.4 Reimbursement

Will subjects be reimbursed for their expenses, such as travel, parking, meals, or any other study related costs?

Yes No Yes No

E. Costs to Subjects

Does the research involve any costs to subjects?

Yes No Yes No

F. Study Design

F.1 Study Timelines

1. *Describe the duration of an individual subject's participation in the study:* one day, maximum 2 hours participation
2. *Describe the duration anticipated to enroll all study subjects at the Tufts study site:* 1 year
3. *Describe the estimated date for investigators to complete this study (complete primary analyses):* December 2019
4. *Describe the study procedures that will be accomplished at each study visit:* At each study visit, subjects in cohorts A, B, and C will undergo a whole-body DXA scan and all subjects will undergo an A-mode ultrasound at 7 anatomical landmarks on the dominant side, using the BodyMetrix Pro ultrasound (Intelametrix, Brentwood, CA).

F.2 Procedures

1. Is there a placebo control arm?
 Yes No Yes No
2. *Provide a description of all research procedures being performed as follows:*
 - a. *How individuals will be screened for eligibility. Specify screening that will take place prior to informed consent and screening that will take place after informed consent:*
 - Cohort A: Healthy volunteers (who may be employees)
 - Potential participants will be asked to confirm age >18 and no history of heart failure
 - Arrangements will be made for a urinary pregnancy test if there is a possibility of pregnancy

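### The stated aim is to validate ultrasound muscle thickness, but no visit item, endpoint or analysis names thickness, so the planned device-FFM comparison cannot by itself support that conclusion

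*Combined protocol and SAP*

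**What the plan says.** Two places say what the study is to establish. Section C, item 1: "The primary objective of this study is to validate the use of ultrasound muscle thickness measurements to determine muscle mass". Section B.3, item 4: "This study will validate the applicability of ultrasound muscle thickness measurements as a method to evaluate muscle mass".

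The hypothesis in Section B.1, item 3 names a different quantity on the DXA side: "We hypothesize that DXA measurements of appendicular lean mass (ALM) will show adequate agreement with skeletal muscle US in systolic HF patients". The same item describes a study of 77 elderly subjects as precedent: "They generated a regression equation using several anatomical ultrasound muscle thickness measurements to predict muscle mass measured by DXA".

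For the visit, Section F.1, item 4 says that "all subjects will undergo an A-mode ultrasound at 7 anatomical landmarks on the dominant side, using the BodyMetrix Pro ultrasound". It does not say what is read at each landmark.

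Section I.1, item 1 pairs DXA FFM with this: "Primary ultrasound endpoint: FFM measured by BodyMetrix ultrasound". Sections I.2 and I.4 plan one analysis, a Bland-Altman comparison of the two FFM values. Section I.4, item 1 adds that the mean difference must lie within +/- 3 (no unit given). The information list in Section I.4, item 5a reads: "Subject number, sex, age, weight, body mass index, heart failure status".

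**The concern.** The objective and the endpoint name different measurements. Muscle thickness is a length read at one site. FFM is a whole-body mass, and seven readings on one side of the body can yield it only through a formula. The protocol does not give that formula, say whether thickness enters it, or say whether body weight does.

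The study could therefore be run exactly as planned, meet its +/- 3 criterion, and still leave open whether muscle thickness measures muscle mass in these patients. If body weight is an input to the device's FFM, some of the agreement with DXA could come from weight rather than from anything the ultrasound sees in muscle. The documents do not settle this either way, so the inputs need to be stated.

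Timing matters. Participation lasts a single day of at most 2 hours, so site readings not stored then may be impossible to recover.

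**Working it through.** The point is not numerical, so the check is to trace muscle thickness through the plan.

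| Place in the protocol | Quantity named | Thickness named? |
|---|---|---|
| B.1 item 3, cited study | Thickness at several sites, entered in a regression equation | Yes, as background |
| B.1 item 3, hypothesis | DXA appendicular lean mass against muscle ultrasound | No |
| B.3 item 4 | Thickness as a measure of muscle mass | Yes |
| C item 1 | Thickness as a measure of muscle mass | Yes |
| F.1 item 4 | A-mode scan at 7 landmarks, quantity unstated | No |
| I.1 item 1 | FFM by DXA, FFM by BodyMetrix | No |
| I.2 item 1, I.4 item 1 | Bland-Altman on FFM, mean difference within +/- 3 | No |
| I.4 item 5a | Demographics, body size, heart failure status | No (FFM is missing too) |

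Outside the reference list, thickness appears in the background, the benefits and the objective. It does not appear where the study is carried out or analysed.

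**What the planned comparison would test.** This depends on how FFM is obtained.

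1. If FFM is the device's own output from unstated inputs, the comparison tests that output. No thickness value is compared with anything.
2. If FFM comes from an existing equation that takes thickness as input and was not fitted in these subjects, the comparison tests thickness and that equation together. This bears on the objective indirectly. The protocol adopts no such equation; the one in B.1 belongs to the cited study.
3. If FFM came from a least-squares equation with an intercept fitted in these same subjects, the residuals would satisfy Σ(DXA − predicted) = 0. The mean difference would be exactly 0 and the +/- 3 rule would be met whatever the data. No passage plans this; it matters only as a limit on any equation added later.

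**Why the existing analysis cannot simply be applied to thickness.** Bland-Altman takes differences between two measurements in the same unit. Thickness is a length and DXA lean mass is a mass, so their difference is not defined. Thickness needs its own analysis, of association or prediction.

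**How many subjects could inform it.** The minimum enrollment reproduces: 3 × 10 (cohorts A to C) + 30 (cohort D) = 60. Section F.1, item 4 gives DXA to cohorts A, B and C only, so the minimum provides 3 × 10 = 30 subjects with both methods. At the maximum of 90, with cohort D held at 30, there would be 90 − 30 = 60.

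**The case against.** The strongest reply is that the plan is silent on the route to FFM, and silence does not show that thickness plays no part. The title of the elderly-cohort study in the reference list concerns predicting fat-free mass from muscle thickness, and B.3, item 4 echoes it. The procedure is called skeletal muscle ultrasound in several places. The team may have meant FFM to be computed from thickness by an existing equation, in which case FFM agreement would be an indirect test of thickness. This stands. A reader might infer that the objective goes untested however the plan is read, and the documents do not support that.

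A reader might also infer from I.4, item 5a that thickness will not be recorded. That does not follow either. The list omits both FFM values, so it is plainly not the full list of measurements. The data collection form mentioned in F.2 is an attachment not available here and may have fields for site thickness. What can be said is that no visit item names thickness.

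Finally, this is a small study meant to produce preliminary data, and B.3, item 3 asks the practical question of whether the hand-held device is comparable to DXA. Device FFM against DXA FFM answers a form of that question. But Section C and B.3, item 4 claim more than that, and B.1 looks ahead to use in later heart failure studies. Even if thickness is recorded, no endpoint or analysis uses it.

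**Conclusion.** The concern holds as a mismatch between the primary objective and the only planned endpoint and analysis. Followed as written, the study yields agreement of BodyMetrix FFM with DXA FFM and cannot by itself support a conclusion about muscle thickness. It would do so indirectly only if FFM were derived from thickness, which the documents do not state.

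The size is qualitative: the wording of the whole primary conclusion is affected, and no figure in the plan changes. The verdict rests on the protocol text alone and assumes nothing about the device's algorithm.

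Two stronger conclusions are not supported. One is that the +/- 3 rule is bound to be met: that is true only of an equation fitted in the same subjects, which is not planned. The other is that agreement would merely reflect body weight: the device's inputs are not given, so no size can be put on this.

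**What to change.** 1. In F.1, item 4, state that muscle thickness is read and stored at each of the 7 landmarks. Add to I.1 and I.2 an analysis of thickness against DXA lean mass in the subjects who have both, naming the DXA quantity used.
2. In I.1, state how BodyMetrix FFM is obtained and from which inputs, including whether body weight enters. Fix this before any DXA-ultrasound pair is examined. Do not apply the +/- 3 rule to an equation fitted in the same subjects.
3. If the device cannot give thickness, reword Section C and B.3, item 4 to claim only agreement of device-estimated FFM with DXA FFM.

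An external thickness equation need not become the primary endpoint. Nothing in the documents shows that the sites, inputs and scan mode of the cited equation match these 7 A-mode landmarks.

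The cost of items 1 and 2 is some form fields, one more analysis and protocol wording, with no extra visit, scan or subject. The cost of item 3 is a narrower claim.
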